3.2 Exclusion criteria

- Patients with KPS $<$ 70%.
- Participation in other studies involving the administration of experimental drugs.
- Any concomitant medical or psychological conditions that could prevent participation in the study or that compromise the ability to provide informed consent.
- Pregnant or breastfeeding patients.

3.3 Methods of recruitment

- Patients belonging to the U.O. of Oncological Radiotherapy, Neurology and Oncology of the ASMN-IRCCS of Reggio Emilia are eligible for participation in the study. After evaluation of eligibility and acquisition of informed consent from the patient, each will be assigned a progressive number which will be used to identify the subject during all phases of the study.

4. OBJECTIVES

4.1 Primary objective

The study proposes the evaluation of the side effects of the proposed experimental radiotherapy treatment and the acceptability of the risk / benefit ratio.

Acute / subacute toxicity will be analysed with recording of adverse events (related or unrelated) reported during the entire treatment and within 3 months of its end.

4.2 Secondary objectives

- Evaluation of the response rate according to the RANO criteria.
- Incidence of treatment-related radionecrosis measured with advanced MRI sequences. More information on the methods followed in the study to make a correct discrimination between radionecrosis and tumor relapses are given in a specific Technical Annex.
- Evaluation (descriptive) of the Quality of Life assessed through EORTC QLQ-C30 and BN20 questionnaires.
- Evaluation (descriptive) of neuro-cognitive functions as indicated in the rest of the protocol.
- Overall survival (OS) assessment.

- Assessment of progression-free survival (PFS).

5. DESIGN OF THE STUDY

It is an exploratory, prospective, experimental, monocentric study.

Having identified a main safety endpoint (toxicity of radiotherapy treatment), and in the absence of data currently available from previous studies and useful for sample sizing, the sample is defined according to criteria of expediency and feasibility, (12 cases), with a design (3 cases + 3 cases + 6 cases) which provides for two intermediate safety assessment steps, one month after the end of treatment for the third and sixth patient. The study will be continued only in the event of a positive evaluation of both steps.

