8.3 Follow-up evaluation

Clinical visits at 7 days, 15 days, 30 days, 60 days and 90 days from the end of radiotherapy (RT).

8.3.1 Mandatory assessments:

- General and neurological examination. A palliative doctor will be supported by the radiotherapist.
- Detection of vital parameters and anthropometric indices.
- Definition of the ECOG and Karnofsky indices.
- Detection of acute / subacute / late toxicity by CTCAE version 4.0 scale.
- Quality of life assessment through EORTC QLQ-C30 and BN20 questionnaires (at 1 and 3 months).
- MRI of the brain before and after m.d.c. paramagnetic (1 month and 3 months from the end of RT).

8.3.2 Optional assessments based on tumor site or patient's particular condition:

- Additional specialist visits (endocrinology, ophthalmology, etc.) according to medical indications.

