12. STATISTICAL ASPECTS

12.1 The champion

The study is proposed as an exploratory, prospective, experimental and monocentric study.

Regarding the main endpoint (toxicity of the proposed radiotherapy treatment), there are no data currently available from previous studies. In the absence of criteria useful for the sizing of the

sample in formal terms, the sample (12 cases) is defined according to criteria of opportunity and feasibility, with two steps of evaluation of the outcome as follows:

- after the first 3 patients enrolled and treated with the proposed radiotherapy scheme, there will be a 1 month stop in the enrollment of subsequent patients, in which tolerance and the occurrence of serious adverse events will be analyzed.
- At the end of the month, if none of the patients treated shows toxicity attributable to radiation treatment > 3, the enrollment of the next 3 patients will continue with a further stop in enrollment for another month.
- If these patients, together with the 3 previously treated, do not have serious adverse events induced by radiation treatment, the enrollment of the last 6 patients will continue.

All patients in the study will be followed, for the primary endpoint of the study, for at least 3 months from enrollment, or until disease progression or death from another cause.

At the end of each intermediate step, the investigator will produce a report on the safety of the cases already treated which will be subjected to the evaluation of an internal board, composed of the Health Director, the Scientific Director and the Legal Doctor of the ASMN-IRCCS of Reggio Emilia, who will express on the continuation / interruption of the study and subsequently notified to the EC.

The internal board will also evaluate any urgent safety measures (as defined in paragraph 11.4) transmitted by the RAV, expressing its opinion on the continuation / interruption of the study and subsequently notifying the EC of this opinion.

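### No pre-specified rule acts on a gate-criterion event that appears after a one-month safety gate but within the three-month primary toxicity window

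*Combined protocol and SAP*

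**What the plan says.** - **Primary window.** Section 4.1 analyses "adverse events (related or unrelated) reported during the entire treatment and within 3 months of its end". Section 8.3 schedules toxicity visits at 7, 15, 30, 60 and 90 days after radiotherapy, and MRI at 1 and 3 months.
- **Gates.** Section 5 sets "two intermediate safety assessment steps, one month after the end of treatment for the third and sixth patient", and continuation depends on both being positive. In section 12.1, after the first three patients, "there will be a 1 month stop in the enrollment of subsequent patients"; a second one-month stop follows the next three.
- **Criteria.** The first gate passes "if none of the patients treated shows toxicity attributable to radiation treatment > 3". The second gate is cumulative: "If these patients, together with the 3 previously treated, do not have serious adverse events induced by radiation treatment", the last six may enrol.
- **Follow-up.** Section 12.1 follows patients for the primary endpoint "for at least 3 months from enrollment, or until disease progression or death from another cause", so it counts from enrolment where section 4.1 counts from the end of treatment.
- **Other safety provisions.** Section 5.2 allows early conclusion if the nature and frequency of events make the risk/benefit ratio unacceptable, with the board working to the section 12.1 plan. Section 10.3 provides safety reports at the 12.1 steps and on request.

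**The concern.** The gates are the plan's main pre-specified protection, and each is decided when its last patient has completed one third of the primary window. A gate-criterion event in months 2-3 in patients 1-3 meets no rule until the second gate, by which time patients 4-6 have been treated. The same event in patients 4-6 meets no later gate, while half the sample (6 of 12) is enrolling.

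This matters because section 2 says no studies give clear indications on acute and late toxicity in previously irradiated tissue, and makes safety the primary objective for that reason. The protocol therefore offers no ground for expecting that gate-criterion events will show themselves within the first month.

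**Working it through.** **Is there a trigger after a gate?**
- Section 12.1 schedules safety reports at the end of each intermediate step only.
- Section 5.2 refers the board back to section 12.1 and sets no threshold or timing.
- Section 10.3 adds reports on request, but does not say what prompts a request.
- Section 11.4, the board's other input, concerns notices and recalls for devices, not patient toxicity.
- Section 10.2 requires the CRF adverse-event section for a serious event, without notice to the board.

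No provision therefore obliges anyone to bring a day-60 or day-90 event to the board or to hold enrolment.

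**How much does a gate miss?** The plan states no toxicity rate, alpha or power, so it has no figure of its own to reproduce beyond 3 + 3 + 6 = 12. The rate p and the timing of events are assumptions.

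*Inputs.* The window is 3 months, and the last patient of each cohort has 1 month at the gate. Even accrual over the stated enrolment period gives 22/12 = 1.83 months per patient (synopsis) or 51/12 = 4.25 (section 5.1); these two periods conflict. One event type is used for both gates.

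*Follow-up at the first gate, patients 1, 2, 3.*
- 22-month plan: 4.67, 2.83, 1.00 months. Capped at 3 and divided by 3, the fractions sum to 1 + 0.944 + 0.333 = 2.278.
- 51-month plan: 9.50, 5.25, 1.00 months. Sum 1 + 1 + 0.333 = 2.333.
- All three treated together: sum 3 × 0.333 = 1.
- Full window: sum 3.

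At the second gate, patients 1-3 are complete under either plan, so the sums are 5.278 and 5.333, against 6 in full.

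*Formula, constant hazard.* P(at least one event seen) = 1 − (1 − p)^(sum of fractions). For one patient seen for one month at p = 0.20: 1 − 0.80^(1/3) = 0.07.

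| Assumed p | First gate, 22 / 51 months | First gate, together | First gate, full | Second gate, 22 / 51 months | Second gate, full |
|---|---|---|---|---|---|
| 0.10 | 0.213 / 0.218 | 0.100 | 0.271 | 0.427 / 0.430 | 0.469 |
| 0.20 | 0.398 / 0.406 | 0.200 | 0.488 | 0.692 / 0.696 | 0.738 |
| 0.30 | 0.556 / 0.565 | 0.300 | 0.657 | 0.848 / 0.851 | 0.882 |

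*Sensitivity to timing.* Let f be the share of events after month 1, with p = 0.20. If only patient 3 is short of follow-up, the first gate detects 1 − 0.80² × (1 − 0.20(1 − f)), which is 0.456, 0.424 and 0.392 for f = 0.25, 0.50 and 0.75. If all three have one month, it detects 1 − (1 − 0.20(1 − f))³, which is 0.386, 0.271 and 0.143. The full-window value is 0.488.

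**How many patients enter during the gap?** With treatment soon after enrolment and 4.25-month spacing, patient 3 passes day 90 before patient 4 enters. With 1.83-month spacing, patient 4 enters before that day and patient 5 (3.67 months after patient 3) does not. The same pattern holds for patients 6, 7 and 8.

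**The case against.** An interim look shorter than the endpoint window is a legitimate design choice. Section 12.1 describes the stops as a review of tolerance and serious adverse events, and nowhere promises that they cover subacute toxicity. The plan is also not silent afterwards: section 5.2 permits early conclusion, section 10.3 permits reports on request, section 11 sends safety reports to the Ethics Committee, and the second gate counts patients 1-3 again. At planned accrual the loss at the second gate is 4 to 5 percentage points at p = 0.20, and at most one patient per gate enters during the gap.

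Most of this stands, and it rules out a stronger reading. A reader might infer that events after a gate cannot stop the next cohort, or that a late event in patients 1-3 cannot be considered before the second gate. The documents do not support that, because sections 5.2 and 10.3 allow action at any time. A reader might also take the 20% detection figure as typical. It requires all three patients to be treated together, which no minimum interval forbids but which is far from 12 patients over 22 or 51 months.

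What remains is that the cover is discretionary. None of these provisions says which late event must reach the board or what happens to enrolment meanwhile, and for patients 4-6 there is no cumulative gate to fall back on.

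**Conclusion.** The gap is real and modest in expected size. As written, no pre-specified rule acts on a gate-criterion event between a one-month gate and the end of the three-month window.

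Under constant hazard and an assumed 20% rate, detection at the first gate falls from 49% to 40-41% at planned accrual, and at the second gate from 74% to 69-70%. At 10%, the first gate falls from 27% to 21-22%. These figures rest on an assumed rate, an assumed event timing and even accrual. The loss grows if events come late or patients within a cohort are treated close together.

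The finding does not show that the one-month stop is wrong or that the study is unprotected after it. It shows that the response to a late event is left to discretion in a study whose primary objective is safety.

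**What to change.** First reconcile two points on which any rule depends: the gate criteria (toxicity above 3 at the first gate, serious adverse events at the second gate) and the start of the window (end of treatment in section 4.1, enrolment in section 12.1). Which versions apply is for the sponsor to decide.

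Then add to sections 5 and 12.1, keeping the one-month stops:

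*If an event meeting the section 12.1 gate criterion is recorded in any of patients 1-6 after a gate and up to that patient's day 90 (or earlier progression, death or withdrawal), the investigator sends a safety report to the internal board, and new enrolment is held until the board gives its opinion.*

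Ending the period at progression, death or withdrawal matters, because some patients will never reach day 90 and a rule that waited for all of them might never close. The rule governs enrolment and board review, not any patient's treatment.

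**Cost.** A few sentences, with existing visits, scans and board. The downside is an occasional extra report, board review and enrolment pause. The alternative of holding each gate until its last patient completes three months would add 2 months per gate, 4 in all: 25 + 4 = 29 months (synopsis) or 54 + 4 = 58 (section 5.1), with accrual otherwise unchanged.

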5.1 Duration of the study

54 months of which 51 for patient enrolment and 3 months for completion of treatment and evaluation of the response of the last patient enrolled.

For each individual patient, the treatment is considered completed if:

- a) the experimental radiotherapy treatment was completed;
- b) the first follow-up radiological evaluation (NMR) was performed;
- c) study treatment was prematurely discontinued due to lack of efficacy (documented disease progression) or unacceptable toxicity.

5.2 Early termination of the study

An internal board will evaluate according to the analysis plan defined in section 12.1 the continuation / interruption of the study in the protection of patients' interests, based on information on the safety of the cases already treated.

The study can be concluded early:

- if the nature and frequency of the events and / or any urgent safety measures are such that the risk and benefit ratio is not acceptable;
- if the number of patients who drop out of the study is such that it is difficult to complete the study.

6. TREATMENT PLAN

6.1 Radiotherapy treatment

The treatment envisaged by the protocol involves the planning and execution of a hypofractionated radiotherapy (RT) treatment, administered in 5 daily sessions, with modulated intensity technique and inhomogeneous distribution of the dose guided by diffusion images obtained with magnetic resonance imaging (MRI).

The radiotherapy treatment must begin within 7 days from the date of execution of the centering MRI which will include both the classic morphological sequences with administration of contrast medium and functional. In this regard, for more details see the Technical Annex.

In selected cases and according to clinical judgment, it will be possible to request a review of the anatomic-pathological and radiological findings.

6.2 Irradiation technique

For each patient, a radiotherapy treatment plan will be carried out with conformed techniques such as intensity modulated radiotherapy (IMRT) with dose redistribution: dose-painting [95 - 97]. More details are described in the Technical Annex.

6.3 Positioning and immobilization of the patient

The patient should be treated in the supine position. The arms should be placed along the body. The use of a knee support is recommended. The head will be immobilized with a thermoplastic mask and corresponding neck rest supports.

6.4 Planning CT and MRI

The planning CT should possibly be acquired with reduced layer thickness that contains the entire volume of the skull and the upper part of the shoulders. This is done to allow for the possibility of planning non-coplanar treatments.

The last follow-up MRI or radiotherapy centering is used for planning, consisting of standard and functional sequences, in addition to those that the neuroradiologist will have considered useful to better characterize the clinical case in question. More details in this regard are described in the Technical Annex.

6.5 Target volume and organs at risk (OAR)

The following target volumes should be identified [98]:

- Gross tumor volume (GTV): is defined using and combining conventional and advanced MR imaging sequences.
- Planning target volume (PTV). It is represented by the GTV with three-dimensional expansion between 0 and 5 mm according to the problems highlighted during the segmentation phase of the tumor. In this regard, for more details see the Technical Annex.

The following primary risk organs (OARs) must be identified:

- Optic nerves. The definition of the related planning risk volume is also suggested (PRV: organ at risk with three-dimensional expansion; this margin must be chosen taking into consideration the acquisition thickness of the centering CT and the chosen GTV-PTV expansion margin)
- Chiasma. The definition of the relative PRV is also suggested (organ at risk with three-dimensional expansion; this margin must be chosen taking into consideration the acquisition thickness of the centering CT and the chosen GTV-PTV expansion margin)
- Retinas. The definition of the relative PRV is also suggested (organ at risk with three-dimensional expansion; this margin must be chosen taking into consideration the acquisition thickness of the centering CT and the chosen GTV-PTV expansion margin).

Alternatively, the eyeballs can be outlined.

- Brain stem.
- The following secondary OARs must be identified:
- Lenses / Crystalline. The definition of the relative PRV is also suggested (organ at risk with three-dimensional expansion; this margin must be chosen taking into consideration the acquisition thickness of the centering CT and the chosen GTV-PTV expansion margin)
- Healthy brain tissue. It is represented by the volume of the brain minus the PTV.
- Ear cochlea. The definition of the relative PRV is also suggested (organ at risk with three-dimensional expansion; this margin must be chosen taking into consideration the acquisition thickness of the centering CT and the chosen GTV-PTV expansion margin).

6.6 Dose prescription

6.6.1 Target dose

The prescription dose provides for a minimum dose of 30 Gy (6 Gy per session) for the areas with the highest ADC, with a gradual increase in the dose for the areas with the lowest ADC. The maximum hypothesized dose is 50 Gy, with a dose of 10 Gy per session at no more than 1cc of irradiated brain tissue. For more details see the Technical Annex.

The treatment plan, however, will be developed according to the following order of priority:

1. Compliance with dose limits for primary OAR.
2. PTV coverage.
3. Compliance with dose limits for secondary OARs.

6.6.2 Dose limits for primary organs at risk

In the scientific literature there are various studies that indicate the dose limits of the organs at risk for cerebral radiotherapy treatments. However, these limitations concern therapies in which conventional fractionations and deliveries to non-irradiated brain tissue are used [bibliography of the studies proposed in Table 1, 98]. The few reports relating to retreatments [99, 100] are mainly addressed to other anatomical areas with poor indications for brain treatments (only the spinal cord and brainstem is mentioned), especially when it comes to hypofractionated techniques as in our case. In retreatments with hypo-fractionation the references refer exclusively to healthy brain tissue. Not being able to use well-coded literature indications, it was decided to refer to the few literature data as well as to the clinical history of our radiotherapy center.

In the work of Ciammella [94] the outcomes of conventional hypofractionated retreatments (5Gy x 5 sessions) on glioblastomas performed at the Reggio Emilia radiotherapy are described both in terms of efficacy and acute toxicity. Therefore the radiotherapist, in the evaluation phase of the dose-painting plans envisaged in this study, will be able to use as an indication and reference of the doses on critical organs estimated for a conventional hypofractionated plan. Since these doses are a function of the anatomical configuration of the patient, as well as of the conformation and position of the tumor recurrence, it is necessary to carry out planning for each individual patient belonging to the study. The final word regarding the clinical approval of the plan to be provided will still be up to the radiotherapist who will clinically evaluate the treatment plan. For more details see the Technical Annex.

6.6.3 Dose limits for secondary risk organs

Also for secondary risk organs, what has been indicated in the previous point (6.6.2) regarding the relative dose limits is valid.

6.7 Changes or suspension of treatment

During the treatment program, neurological toxicities will be evaluated according to criteria of the National Cancer Institute Common Toxicity Criteria for Adverse Events (NCI CTCAE), version 4.0. The patient will be monitored for the appearance of adverse events for the entire duration of the study, including the follow-up period.

Events	Actions
a) Neurological toxicity \leq grade 2 responsive to supportive care b) Grade \leq 3 non-neurological toxicity	The RadioTherapy treatment continue
c) grade $>$ 3 neurological and non-neurological toxicity; d) grade \leq 2 neurological toxicity unresponsive to supportive care; e) disease progression during treatment; f) second medical opinion, for safety reasons; g) refusal of the patient to continue the treatment; h) need to start antineoplastic therapy.	The presence of at least one of the events determines the definitive suspension of the treatment. It also involves leaving the study in cases (e) and (h)

In case of grade \leq 2 neurological toxicity with response to adequate supportive therapy (steroids, mannitol, anticomitials) the radiotherapy treatment will continue.

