7. EXIT FROM THE STUDY AND SUSPENSION OF THE TREATMENT

7.1 Exit from the study

Should one of the following conditions occur, the patient should be considered off-study and will not be included in the study's end point analysis:

- a. refusal of the patient to continue the treatment (withdrawal of informed consent);
- b. violation of the inclusion / exclusion criteria.

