7.2 Suspension of treatment

Treatment must be permanently suspended if one or more of the following situations occur:

- grade > 3 neurological and non-neurological toxicity;
- grade ≤ 2 neurological toxicity unresponsive to supportive care;
- disease progression during treatment;
- second medical opinion, for safety reasons;
- refusal of the patient to continue the treatment;
- need to start antineoplastic therapy.

Permanent discontinuation of treatment, in case of disease progression or unacceptable toxicity, will be considered as a therapy failure, therefore patients will be included in the study's end-point analysis.

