13.3 Monitoring and Quality Control (QC)

Through an electronic e-CRF set up on a web platform by the IT Service of the ASMN-IRCCS company, of Reggio Emilia (promoter of the study), the registration of patients entering the study and the availability of clinical data will be guaranteed with continuity.

The Clinical Studies and Statistics Office will propose a monitoring program suitable for the type of study in accordance with the company SOPs with centralized monitoring actions, off site and on site, managed by adequately trained staff.

In the event of early termination of treatment, patients will still be monitored for the entire duration of the study or for any documented disease progression, death or exit from follow-up.

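### Section 6.7 takes patients who progress on treatment or need antineoplastic therapy out of the study; sections 7.1, 7.2, 9 and 13.3 do not, leaving OS, and for new therapy also PFS and toxicity, open to loss

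*Combined protocol and SAP*

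**What the plan says.** The action table in section 6.7 lists events that end treatment for good. Two of them are "e) disease progression during treatment" and "h) need to start antineoplastic therapy". For these two only, it adds: "It also involves leaving the study in cases (e) and (h"). Refusal to continue, event (g), stops treatment without that addition.

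Other sections deal with the same patients as follows.

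- **Section 7.1** defines exit. Under its conditions, "the patient should be considered off-study and will not be included in the study's end point analysis". There are two conditions: an eligibility violation, and "refusal of the patient to continue the treatment (withdrawal of informed consent"). Neither (e) nor (h) is listed.
- **Section 7.2** repeats the events of 6.7 as reasons to suspend treatment, with no mention of leaving the study. It then says: "Permanent discontinuation of treatment, in case of disease progression or unacceptable toxicity, will be considered as a therapy failure", and keeps those patients in the end-point analysis. It does not say how (h) is analysed.
- **Section 7.3** requires a visit within 7 days of stopping, except after death or withdrawn consent.
- **Section 9** considers for analysis every patient who began radiotherapy. After an early stop, this runs to the scheduled follow-up visit.
- **Section 12.1** follows patients for the primary endpoint for at least 3 months from enrolment, or to progression or death.
- **Section 12.2** specifies Kaplan-Meier for OS and PFS but gives no event or censoring rule.
- **Section 13.3** says that after an early end of treatment "patients will still be monitored for the entire duration of the study or for any documented disease progression, death or exit from follow-up".

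**The concern.** The protocol does not keep off-treatment and off-study apart, so one patient can have two statuses. If leaving the study in 6.7 means off-study in the sense of 7.1, the patient drops out of the end-point analysis, against 7.2 and section 9. If it means only that follow-up ends, the patient is censored at that point.

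Progression within the course, or a need for other anticancer treatment, plausibly marks a poor prognosis. Censoring there is therefore likely to be informative, and exclusion removes likely failures. Either way the estimates lean towards a better result than the treatment gave. Because 12.2 sets no censoring rule, the choice would be made at analysis with outcomes known.

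The primary endpoint is touched too. Section 4.1 collects adverse events to 3 months after treatment, and 12.1 ends that follow-up at progression or death, not at new therapy. An (h) exit would cut short data that 12.1 requires.

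**Working it through.** The plan gives no error rate or event rate to reproduce. The sample size of 12 is set by feasibility, and 3 + 3 + 6 = 12 agrees. The main check is a comparison of the sections.

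**Step 1. Status of the same patient by section**

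| Section | (e) progression | (h) new antineoplastic therapy | (g) refusal |
|---|---|---|---|
| 6.7 | stops treatment, leaves study | stops treatment, leaves study | stops treatment only |
| 7.1 | not an exit | not an exit | exit, out of analysis |
| 7.2 | suspended, kept as failure | suspended, analysis status not stated | suspended, analysis status not stated |
| 9 | considered if radiotherapy started | same | same |
| 12.1 (toxicity) | may end at progression | at least 3 months | at least 3 months |
| 13.3 | can be read as ending at progression | monitoring continues | monitoring continues unless refusal is an exit |

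Section 6.7 conflicts with 7.1 on both (e) and (h). It conflicts with 13.3 clearly for (h) and less clearly for (e). Sections 6.7 and 7.1 treat refusal in opposite ways.

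**Step 2. What is lost if 6.7 is followed**

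- (e), PFS: the event is the reason for exit, so it is already documented. It is lost only if exit is read as exclusion under 7.1.
- (e), OS: later death may go unrecorded.
- (h), PFS and OS: with no progression recorded, the patient can be excluded or informatively censored for both.
- (h), toxicity: the rest of the 3-month assessment can be lost.

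**Step 3. How many patients through (e)**

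Inputs: 12 patients; median PFS m from 2.6 to 10.5 months (lowest and highest in Table 1); five daily sessions, assumed to span d = 5 to 7 calendar days. Progression times are assumed exponential, with 30.4375 days per month.

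Chance per patient: p = 1 − 2^(−(d/30.4375)/m). Chance of at least one of 12: 1 − (1 − p)^12.

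- m = 10.5, d = 5: p = 1.08%; at least one of 12 = 12.2%; expected 12 × 0.0108 = 0.13 patients.
- m = 2.6, d = 7: p = 5.95%; at least one of 12 = 52.1%; expected 12 × 0.0595 = 0.71 patients.

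The documents give nothing from which the frequency of (h) could be estimated.

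**Step 4. Effect of one lost failure**

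Assumed counts: one early exit that would count as a failure by 3 months, k other events after the exit, and no other censoring. Kept as a failure, the event-free proportion is (11 − k)/12. Removed, or censored at exit, it is (11 − k)/11.

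- k = 0: 11/12 = 91.7% becomes 11/11 = 100%, +8.3 points.
- k = 3: 8/12 = 66.7% becomes 8/11 = 72.7%, +6.1 points. The Clopper-Pearson 95% intervals are 34.9 to 90.1 and, with the patient removed, 39.0 to 94.0.
- k = 6: 5/12 = 41.7% becomes 5/11 = 45.5%, +3.8 points.

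With two exits and k = 3, 7/12 = 58.3% becomes 7/10 = 70.0%.

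**The case against.** The strongest reply is that the rest of the protocol limits the damage.

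- Section 7.2 counts progressors as failures in the analysis, and section 9 considers everyone who began radiotherapy. This stands in part: it protects the PFS event for (e) and weakens any claim that (h) has no analysis status. It does not secure survival follow-up, and section 9's window after an early stop runs only to a scheduled visit.
- A reader might infer that 6.7 ends all data collection. The text does not say so. Section 6.7 itself monitors adverse events through the follow-up period, and the 7.3 visit covers both (e) and (h).
- A reader might infer that 13.3 contradicts 6.7 for both events. Its mention of documented progression allows monitoring to end there, so the contradiction is clear only for (h).
- A reader might fear different practice between sites. The study is monocentric; the risk is inconsistent application by staff or by the analyst.
- Taking medians of 3 to 5 months and a 7-day course gives 32% to 47% for at least one (e) patient. That is a selected part of Table 1. Mandatory MRI falls at 1 and 3 months after treatment, with none scheduled during the sessions, so recorded cases would probably be fewer than any of these figures.
- OS and PFS are secondary, untested and only briefly described, and the continuation decisions rest on toxicity.

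These points reduce the size of the problem. None of them removes the conflict over who leaves the study.

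**Conclusion.** The inconsistency is real and should be corrected. Followed literally, 6.7 can lose OS follow-up after (e) and (h), and it can remove (h) patients from PFS and from the 3-month toxicity assessment. The stronger reading, that clear failures drop out of both OS and PFS whichever event occurs, is not supported: for (e) the PFS event is known at exit and 7.2 keeps it, unless exit is taken to mean exclusion.

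The size is modest. Through (e) it is probably 0 or 1 patient, with a 12% to 52% chance of at least one, resting on exponential progression, the Table 1 medians and a 5 to 7 day course. The number through (h) is unknown. Each lost failure moves a 3-month event-free estimate by about 4 to 8 points; 8.3 is the maximum for a single exit and needs no other events. The effect is well inside the confidence interval, but it runs in one direction.

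**What to change.** Leave the treatment-suspension rules as they are and change only study status, data collection and analysis.

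1. In 6.7, delete the sentence on leaving the study, so that (e) and (h) are off-treatment and not off-study.
2. In 7.2, name (h) among the stops kept in the end-point analysis, in line with section 9.
3. State that vital status is still collected for OS after (e) and (h).
4. In 12.2, make (e) a PFS event on its date and pre-specify one PFS rule for (h). For example, follow to documented progression or death, with a sensitivity analysis that counts the start of new therapy as an event.
5. Continue toxicity collection to 3 months after (h), as 12.1 already requires. Reconcile 12.1 and 13.3 on whether toxicity follow-up continues after progression.
6. Reconcile refusal in 6.7(g) and 7.2 with 7.1, separating refusal of treatment from withdrawal of consent.

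The cost is protocol wording in these sections and continued contact with perhaps one or two patients. OS and PFS may look slightly less favourable.
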